6.1 Effectiveness Endpoints

6.1.1 Primary Effectiveness Endpoint

The primary effectiveness endpoint is the proportion of responders at Week 8, as assessed live by a blinded evaluator. A responder is defined as a subject with at least 1-point improvement from baseline on MIHAS of both IOHs. For baseline, the MIHAS scores as assessed at Screening will be used. Further details on assessments and visits used for analysis are described in detail in Section 5.1.1.

The primary effectiveness endpoint will be analyzed based on the ITT population. The proportion of responders at Week 8 will be summarized as counts and percentages for the pooled TRT and the pooled CTL groups. For analyses based on multiple imputation as described below, the average number and percentage of responders, over all imputations, will be presented instead. Four hypothesis tests will be performed and will be evaluated in sequential order. The formal hypotheses of each test are given in \square To control for multiplicity, a hierarchical-testing procedure will be performed. Each test will hereby be performed at a one-sided α level of 0.025.

The first two tests for the primary endpoint of treatment versus control will be confirmatory tests as outlined in column and as described in detail in Section 6.1.1.1; if both null hypotheses are rejected, two additional tests will be performed, as confirmative subgroup analyses, to separately investigate the effectiveness of the two injection techniques (i.e., needle and cannula). For the subgroup analyses, the first test is TN vs. CTL and only if this hypothesis can be rejected, the test of TC vs. CTL will be performed. Details on this subgroup analysis are given in Section 6.1.1.3.

6.1.1.1 Primary analysis

The first hypothesis test of the primary analysis evaluates whether the response rate at Week 8 (Visit 3) in treated subjects is significantly larger than 50%. The analysis will be based on all subjects of the ITT population in the TRT treatment group.

Hypothesis test 1:

 H_{10} : $\pi_{TRT} \leq 50\%$

 H_{11} : $\pi_{TRT} > 50\%$,

where π_{TRT} denotes the responder rate in percent at Week 8 of treated subjects.

The second hypothesis test evaluates whether the response rate in treated subjects at Week 8 (Visit 3) is higher than the response rate in untreated subjects at Week 8 (Visit C1-a). The analysis will be based on all subjects from the ITT population in the TRT and CTL groups.

Hypothesis test 2:

 H_{20} : $\pi_{TRT} \leq \pi_{CTL}$

 H_{21} : $\pi_{TRT} > \pi_{CTL}$,

where π_{TRT} and π_{CTL} denote the responder rates in percent at Week 8 of the treated and untreated subjects, respectively.

Both hypotheses will be tested using the lower limits of the 95% CIs (two-sided), based on Wilson scores. The lower limit of the 95% Wilson CI for the responder rate in the TRT group must exceed the margin of 50% responder rate to reject Hypothesis 1 (H_{10}). The lower limit of the 95% Newcombe CI for the difference between the responder rates in the TRT and the CTL groups (TRT-CTL) must be greater than zero to reject Hypothesis 2 (H_{20}).

Using the Wilson and Newcombe CIs in these tests will allow for imputation of missing values of the primary effectiveness endpoint with a multiple-imputation approach. This procedure will replace missing MIHAS values at Week 8 for the ITT population.

SAS PROC MI will be used to create 100 sets with imputed MIHAS scores per treatment group (TRT and CTL) and per IOH (left and right). For each treatment group and IOH, a different seed will be used for implementation. For treatment group TRT, a seed of 2793 and a seed of 8210 will be used for left and right IOH, respectively. Regarding the control group CTL, a seed of 3913 and a seed of 7956 will be used for left and right IOH, respectively. Baseline MIHAS, Week 4 (Visit 2-a) MIHAS, (pooled) site, and touch-up (yes/no) will be included in the multiple-imputation model for subjects in the TRT group. Details on pooling of sites are described in Section 6.4.5. If Week 4 MIHAS scores are missing, then these will be imputed using the same covariables available up to the respective time point, before imputing Week 8 MIHAS scores. Baseline MIHAS and (pooled) site will be included in the multiple-imputation model for subjects in the CTL group. The default number of burn-in iterations before each imputation (20) will be used for all imputation models. In order to ensure reproducibility, the data will be sorted by subject identifier (USUBJID) prior to imputation. SAS code similar to the following will be used:

Subsequently, it will be determined for each subject within each of the imputed datasets, whether response is achieved at Week 8 $(\ge 1$ -point improvement from baseline on MIHAS of both IOHs).

This code assumes that 'response' is coded with '1' and 'no response' is coded with '0'. Moreover,

This code assumes that 'response' is coded with '1' and 'no response' is coded with '0'. Moreover, midata_8w_trt_left, midata_8w_trt_right, midata_8w_ctl_left and midata_8w_ctl_right are the subsets of midata_trt_left, midata_trt_right, midata_ctl_left and midata_ctl_left, respectively, and will include only the MIHAS scores at baseline and at Week 8.

For the Hypothesis Test 1, the Wilson CI for the response rate in the TRT group ($[WL_{TRT}, WU_{TRT}]$) will be calculated using the following steps, as detailed in [1]:

1. The mean sample response \hat{p}_{Imp} and sample variance $\widehat{U}_{Imp},$

$$\widehat{U}_{Imp} = \frac{\widehat{p}_{Imp} (1 - \widehat{p}_{Imp})}{n},$$

will be calculated for each of the m=100 imputed datasets with sample size n.

2. The overall mean \bar{p}_m and variance \bar{U}_m over all imputed datasets will be calculated:

$$\bar{p}_m = \frac{1}{m} \sum_{lmp=1}^m \hat{p}_{lmp},$$

$$\bar{U}_m = \frac{1}{m} \sum_{lmp=1}^m \hat{U}_{lmp}.$$

These will be used to obtain B_m ,

$$B_m = \frac{1}{m-1} \sum_{lmp=1}^{m} (\hat{p}_{lmp} - \bar{p}_m)^2$$

the between-sample variance.

3. The two boundaries of the Wilson CI (WLTRT and WUTRT) will be calculated as

$$\frac{2\overline{p}_{m} + \frac{t^{2}}{n} + \frac{t^{2}r_{m}}{n}}{2\left(1 + \frac{t^{2}}{n} + \frac{t^{2}r_{m}}{n}\right)} \pm \sqrt{\frac{\left(2\overline{p}_{m} + \frac{t^{2}}{n} + \frac{t^{2}r_{m}}{n}\right)^{2}}{4\left(1 + \frac{t^{2}}{n} + \frac{t^{2}r_{m}}{n}\right)^{2}} - \frac{\overline{p}_{m}^{2}}{1 + \frac{t^{2}}{n} + \frac{t^{2}r_{m}}{n}}},$$

where t denotes the 0.975 quantile of the t-distribution with v degrees of freedom,

$$v = (m-1)\left(1+\frac{1}{r_m}\right),\,$$

and with

$$r_m = \left(1 + \frac{1}{m}\right) \frac{B_m}{\overline{U}_m}.$$

 In order to reject Hypothesis 1 (H₁₀), the lower limit of the 95% Wilson CI as given above, which results from the complete multiple imputation procedure must exceed the margin of 50%.

For the test of Hypothesis 2, the Newcombe CI will be calculated using the following procedure (as described in [2]), assuming ignorable missingness:

[figure not shown]
- The 95% Wilson CIs will be calculated for groups TRT and CTL as described above, denoted as [WL_{TRT}, WU_{TRT}] and [WL_{CTL}, WU_{CTL}] with upper and lower bounds WL_{TRT}, WU_{TRT}, WL_{CTL}, WU_{CTL}.
- The lower and upper bound of the Newcombe CI will then be computed using the following formulas

$$\begin{aligned} NL &= \bar{p}_{m,TRT} - \bar{p}_{m,CTL} - \sqrt{\left(\bar{p}_{m,TRT} - \text{WL}_{TRT}\right)^2 + \left(\text{WU}_{CTL} - \bar{p}_{m,CTL}\right)^2}, \\ NU &= \bar{p}_{m,TRT} - \bar{p}_{m,CTL} + \sqrt{\left(\text{WU}_{TRT} - \bar{p}_{m,TRT}\right)^2 + \left(\bar{p}_{m,CTL} - \text{WL}_{CTL}\right)^2}, \end{aligned}$$

where $\bar{p}_{m,TRT}$ and $\bar{p}_{m,CTL}$ are the overall means for TRT and CTL groups, respectively (see step 2 in the calculation of the Wilson CI).

 The lower limit NL of the calculated two-sided 95% Newcombe CI must be greater than zero to reject Hypothesis 2 (H₂₀).

If both hypotheses H₁₀ and H₂₀ are rejected, two additional tests will be performed as subgroup analyses (see Section 6.1.1.3).

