During the baseline and subsequent study visits, subjects will be evaluated live on the MIHAS by a trained evaluator (i.e., a qualified healthcare practitioner delegated by the treating investigator); this evaluator is blinded to the subject's treatment assignment and will perform the respective assessment independently from any study staff. Prior to study enrollment, at least one blinded evaluator at each site will be trained and qualified by the study sponsor to perform scale-grading assessments. Training will consist of an instructional session, followed by a qualification where blinded-evaluator trainees will score two sets of photographs, representing a variety of different MIHAS grades, at least two weeks apart. The purpose of this assessment is to obtain intra- and inter-evaluator reliability qualification analyses prior to starting the study at their respective site (i.e., weighted Kappa/ICC analyses). Any blinded evaluator who does not successfully achieve an intra- and inter-rater (pair-wise against other raters) reliability point estimate value of ≥ 0.70 will be retrained and requalified up to two times. If evaluator retention (e.g., change in personnel) becomes an issue during the study, new blinded evaluators must be trained by the sponsor, and respective qualification analyses must be performed. Qualification and training of blinded evaluators will be documented. At each study site, all efforts should be made to plan for and maintain the same blinded evaluator for all assessments throughout the study. To account for illness or unplanned absence of the blinded evaluator, it is recommended to have at least one back-up blinded evaluator trained and qualified per site. Evaluators will be re-trained on the MIHAS at regular intervals (approximately every 3 months at a minimum).

The treating investigator will also attend a MIHAS-instructional session to ensure understanding of the subject-eligibility criteria of right and left IOH volume deficit with a rating of 2 or 3 (moderate or severe) at study entry.

Additionally, three blinded IPRs will assess subject photographs using the MIHAS.

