13.4.1.1 Primary Effectiveness Endpoint

The primary effectiveness endpoint (Section 7.2.1.1) will be summarized as counts and percentages for the pooled treatment group (TRT) and the pooled control group (CTL).

Four hypothesis tests will be performed, based on the primary effectiveness endpoint. These tests will be evaluated in a sequential order on the $ITT_{(1)}$ population. To control for multiplicity, a hierarchical-testing procedure will be performed. Each test will hereby be performed at a one-sided α level of 0.025. The first two tests for the primary endpoint of treatment versus control will be confirmatory tests as outlined in the primary endpoint of th

[figure not shown]
Primary analyses

The first hypothesis test of the primary analysis evaluates whether the response rate in treated subjects from TRT is significantly larger than 50%. The second hypothesis test evaluates whether the response rate in treated subjects from TRT is higher than the response rate in untreated subjects from the control group CTL. Both hypotheses will be tested using the lower limits of the 95% CIs (two-sided), based on Wilson scores. The lower limit of the 95% Wilson CI must exceed the margin of 50% responder rate to reject Hypothesis 1 (H₁₀). The lower limit of the 95% Newcombe CI must be greater than zero to reject Hypothesis 2 (H₂₀).

Using the Wilson and Newcombe CIs in these tests will allow for imputation of missing values of the primary effectiveness endpoint with a multiple-imputation approach. This procedure will replace missing MIHAS values at Week 8 for the ITT₍₁₎ population.

SAS PROC MI will be used to create multiple sets with imputed MIHAS scores per group. Baseline MIHAS, Week 4 MIHAS, pooled site (for pooling details, see subgroup analyses below) and touch-up (yes/no) will be included in the multiple-imputation model. For each data set, the Wilson CI will be computed and later combined using SAS PROC MIANALYZE. Then, the limits of the two resulting combined Wilson CIs for TRT and

CTL will be used to compute the Newcombe CI for the responder rate difference between the groups.

[figure not shown]
Subgroup analyses

If both alternative hypotheses in the primary analysis are accepted, additional hypotheses testing will be performed to evaluate whether treatment with cannula-injection technique and treatment with needle-injection technique are superior over control as displayed in test Steps 3 and 4.

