The time in weeks from randomization until premature discontinuation from study up to Week 8 will be displayed using a Kaplan-Meier curve. This curve will be provided for subjects in TRT and CTL groups based on all subjects randomized. Subjects who do not discontinue the study within the specified time window will be presented as censored at the date of their Week 8 visit. Subjects in TRT group that missed their Week 8 visit but did not discontinue will be censored at the target day of the Week 8 visit (i.e. Day 57 after last injection in treatment Cycle 1). For subjects who attended only visits up to Week 8 with date of last contact after Week 8, the date of discontinuation will be set to the date of the Week 8 visit.

The time in months from first treatment until premature discontinuation from study will be described by a second Kaplan-Meier curve for the TRT and DTRT groups in SP. Subjects who complete the study will be presented as censored at end of study.

Visit attendance (subjects expected at visit, subjects with visit performed on-site, subjects with visit performed virtually, subjects with missed visit due to COVID-19 pandemic or other reasons, subjects discontinued) will be presented in a frequency table for various treatment groups (i.e., TN, TC, TRT, CDTN, CDTC, CDTRT) based on all randomized subjects.

For 'Study discontinued', the cumulative number of subjects who discontinued the study before the respective visit will be displayed. For 'Subjects expected at visit', the following visits are defined as expected for all randomized subjects: Screening visit, initial treatment visit V1-a, V1-b, V2-a, V3 – V7-a, V8, V9 for TRT subjects; and Screening visit, visits C1-a, C1-b, C2-a, C3 and all following visits for CDTRT subjects, as defined in the visit schedules in the CSP column for TRT subjects and column for CDTRT subjects). Visits V2-b/C2-b and V2-c/C2-c are

only expected for subjects receiving an optional touch-up at visit V2-a/C2-a. In case of retreatment at visit V7-a for TRT subjects, follow-up visits V7-b and V7-c are also expected. For subjects who discontinue the study, the end of study visit V9/C7 is expected. Visits after premature discontinuation are generally not expected. The number of 'Subjects expected at visit' is thus calculated as number of randomized subjects – the number of subjects discontinued before the respective visit.

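### The Week 8 imputation model for treated subjects uses no MIHAS rating after Visit 2-a, so an available Week 12 (V4) rating is left unused

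*SAP*

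**What the plan says.** SAP 6.1.1.1 defines the treated-group model: "Baseline MIHAS, Week 4 (Visit 2-a) MIHAS, (pooled) site, and touch-up (yes/no) will be included in the multiple-imputation model". Protocol 13.4.1.1 has the same content, beginning "Baseline MIHAS, Week 4 MIHAS, pooled site" and adding touch-up. Left and right IOH are imputed separately. The order runs forward in time: a missing Week 4 score is filled first, from "covariables available up to the respective time point, before imputing Week 8 MIHAS scores". The Newcombe interval for the second hypothesis is computed "assuming ignorable missingness".

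The documents also provide for the subjects in question. Under Disposition of subjects the SAP has a rule for a treated subject with no Week 8 visit who remains in the study: "Subjects in TRT group that missed their Week 8 visit but did not discontinue will be censored at the target day". Protocol 11.2.1.1 describes live rating beyond Week 8: "During the baseline and subsequent study visits, subjects will be evaluated live on the MIHAS by a trained evaluator". SAP 6.4.1 puts V3 at Day 57 and V4 at Day 85 after the last injection. Retreatment is offered only at 48 weeks, so no injection is planned between V3 and V4. Visits V2-b and V2-c are "only expected for subjects receiving an optional touch-up at visit V2-a/C2-a".

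**The concern.** The V4 rating is made on the same scale, under the same injection, four weeks after the missing one. It should predict the Week 8 score better than a Week 4 score does, above all when a touch-up came after Week 4. Leaving it out makes ignorable missingness harder to defend, because missingness that depends on later status is then not conditioned on. It also leaves avoidable between-imputation variance.

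The same imputed data sets feed all four hierarchical tests, so an overstated treated rate would carry through to the 50% margin test, the comparison with control, and the needle and cannula comparisons.

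**Working it through.** **Plan's own figures.** A one-sided exact binomial test with n = 80 against 50% has critical count 50 (exact level 0.0165) and power 94.1% at a 70% rate. Fisher's exact test with 80 vs 40 subjects and 70% vs 30% has power 98.4%. The product is 0.941 × 0.984 = 92.6%, and 120/(1 − 0.20) = 150. The SAP states at least 94%, at least 98%, above 92%, and 150. All reproduce. The point concerns what is in the imputation model and does not disturb these figures.

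**Which ratings reach the model** (SAP 6.1.1.1 and 6.4.1; days count from the last injection, and no regular visit fills the slot):

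| Treated subject without a V3 rating | Handling |
|---|---|
| Discontinued, end-of-study rating Day 44–71 | Assigned to V3: has a Week 8 value, not imputed |
| Discontinued, no touch-up, Day 23–43 | Assigned to V2-a: can enter as the Week 4 score |
| Discontinued, touch-up given, Day 23–43 | Assigned to V2-c: not in the model |
| Discontinued, Day 72–127 | Assigned to V4: not in the model |
| Continuing, rated at V4 | No reassignment: not in the model |

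A discontinued subject's rating on Day 71 thus counts as the Week 8 outcome, while one on Day 72 does not enter even as a predictor.

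The documents give neither the number of affected subjects nor the correlations between visits. Everything below rests on assumed values.

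**Precision.** Take n = 100, response 70%, about 15 missing V3, 80% of those rated at V4, and a latent Week 8–12 correlation of 0.8 to 0.97. Under missingness at random the relative variance increase r falls from about 0.16 to between 0.12 and 0.08 when V4 is added. In the SAP's Wilson formula put a = t²(1 + r)/n. The lower limit is (2p + a)/(2(1 + a)) − √[(2p + a)²/(4(1 + a)²) − p²/(1 + a)].

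- r = 0.16: 59.6%.
- r = 0.08: 60.0%.
- The standard error changes by √(1.12/1.16) = 0.98 to √(1.08/1.16) = 0.96, that is, by 2% to 4%.

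**Bias if missing V3 is related to the later rating.** A simulation of 200,000 subjects used latent correlations of 0.5–0.7 (Week 4–8) and 0.7–0.9 (Week 8–12).

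- Missingness unrelated to the later rating: bias 0.05 points or less.
- Later non-responders with three times the odds of missing V3: the treated rate is overstated by 0.4–0.8 points at 5% missing and 0.9–1.5 points at 10% missing. Adding the later rating for all of them removes this.
- At about 13% missing, a separate calculation gives 1.3–2.0 points, falling to 0.3–0.4 with V4 added.

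**Bias if missing V3 is related to the unseen Week 8 outcome.** Suppose 30% of non-responders and 8% of responders miss V3.

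- Missing: 0.30 × 0.30 + 0.70 × 0.08 = 14.6%.
- Observed rate: (0.70 × 0.92)/(0.70 × 0.92 + 0.30 × 0.70) = 0.644/0.854 = 75.4%, an excess of 5.4 points before any covariate helps.
- With the current model the excess is about 4.5–5.1 points. With V4 added it is about 2.4–4.0, depending on the correlation.
- If only 60% of them are rated at V4 and the correlation is 0.6–0.8, the reduction is only 0.1–0.5 points.

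**Bound on the first test.** Let k of 100 treated subjects miss V3 and be rated later. All others respond at 70%, and the k are imputed at about that rate, giving 70/100 and a complete-data Wilson lower limit of 60.4%. If every later rating pointed to non-response, the rate would be (100 − k) × 0.70:

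- k = 5: 66.5%, lower limit 56.8%.
- k = 10: 63.0%, lower limit 53.2%.
- k = 15: 59.5%, below the 60/100 needed to clear the 50% margin.

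**The case against.** The strongest reply is that few subjects are affected and the plan already reduces their number. SAP 6.4.1 gives some discontinued subjects a Week 8 or Week 4 value. Protocol 9.2.5 requires missed visits to be rescheduled, and protocol 11.3 allows wider windows in a pandemic. A subject lost before V3 has no V4 rating to use. The censoring rule shows that a missed V3 without discontinuation was foreseen, not that it is common. All of this stands, and it limits the size of the point. It does not alter what the model omits.

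Some stronger readings are tempting but not supported:

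- A reader might infer that every rating outside V3 is ignored. The Day 44–71 and Day 23–43 reassignments show otherwise.
- A reader might infer that a Week 12 non-responder is imputed at about the arm's 70% rate. The model conditions on baseline, Week 4 score, site and touch-up. On the assumptions tried, the mean imputed probability for such a subject is between 52% and 69%, and lower for one who had also not responded at Week 4. That is still too high, but it is not the arm average.
- A reader might want V2-c added as well. V2-c is planned only for touched-up subjects, so it is absent by design for the rest and cannot simply be put into the same imputation call.

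The visit-by-visit schedule, the imputation code and SAP 6.1.1.2 are not in the text available. That MIHAS is rated at V4 therefore rests on the general statement in protocol 11.2.1.1, and a sensitivity analysis using later ratings cannot be ruled out. Neither gap is a fault in the plan.

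**Conclusion.** The point holds as an inexpensive improvement to the primary imputation. It is not a threat to the trial's conclusion at the planned rates. The treated-group model discards a V4 rating that may be available for a continuing subject who missed V3, or for a discontinued subject rated on Day 72 to 127. For touched-up subjects it relies on a post-injection score taken before the touch-up, and the touch-up indicator corrects for this only on average.

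The precision lost is small. The overstatement of the treated rate is roughly 0.4 to 2 points if missing V3 tracks later non-response with 5% to 13% missing. It is larger if missingness tracks the unseen Week 8 outcome, and V4 then repairs only part of it. If missing V3 is unrelated to the later rating, there is no material bias. At a 70% rate the first test would be at risk only in the extreme case of about 15 such subjects per 100, all non-responders. These sizes rest on assumed missingness and correlations, and the number affected is unknown.

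**What to change.** In SAP 6.1.1.1 and protocol 13.4.1.1, add the V4 (Week 12) MIHAS of the same IOH as an auxiliary variable in the imputation model for the treated group. State that it includes end-of-study ratings assigned to V4 under SAP 6.4.1. Keep the site-pooling rule of SAP 6.4.5 for convergence problems. Leave the control model unchanged, because controls are injected after their C1-a assessment and their later ratings describe a treated state.

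The cost is one more incomplete covariate to impute and a slightly higher chance of convergence problems, with about 100 treated subjects across up to 9 sites. No new data are needed. Protocol section 13 allows such changes by amendment to the protocol or SAP, with the SAP finalized before database close.

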11.2.1.1 Merz Infraorbital Hollow Assessment Scale (MIHAS)

The MIHAS was designed to assess the infraorbital hollow that results from volume loss. Each grade of the MIHAS is distinct; Grade 0 is anchored to depict none to minimal signs of hollowing, and Grade 4 is anchored to depict extreme signs of hollowing

In the current study, the MIHAS will be used to detect clinically relevant, aesthetic changes as a result of volume correction in the IOH area.

For each of the five severity grades presented on the scale, three reference subjects are displayed. For each subject, a frontal view is presented to indicate specific characteristics of the IOH region. The left and right IOH of each subject is assessed independently on the MIHAS within this study.

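### SAP 6.1.1.1 names the left-side control data set twice, so the right-side control Week 8 set is described as left-side data; very probably a naming slip, to be corrected and checked in the program

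*SAP*

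**What the plan says.** The responder rule is in SAP 6.1.1: "A responder is defined as a subject with at least 1-point improvement from baseline on MIHAS of both IOHs". SAP 6.1.1.1 then sets out how missing Week 8 scores are filled in. PROC MI creates 100 sets with "imputed MIHAS scores per treatment group (TRT and CTL) and per IOH (left and right"), and each combination has its own seed. For controls: "Regarding the control group CTL, a seed of 3913 and a seed of 7956 will be used for left and right IOH, respectively".

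Response is then determined for every subject in every imputed data set, again on both hollows. A note to the SAS code explains the data-set names: "midata_8w_trt_left, midata_8w_trt_right, midata_8w_ctl_left and midata_8w_ctl_right are the subsets of" four source sets, and the sentence continues that they "are the subsets of midata_trt_left, midata_trt_right, midata_ctl_left and midata_ctl_left, respectively". Each Week 8 set "will include only the MIHAS scores at baseline and at Week 8". The SAS code that the note belongs to does not appear in the public text.

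Protocol 11.2.1.1 states: "The left and right IOH of each subject is assessed independently on the MIHAS within this study".

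**The concern.** Read in order, the note pairs `midata_8w_ctl_right` with `midata_ctl_left`. The control right-side imputed set, created under seed 7956, does not appear in the list. Nothing else in the protocol or SAP corrects this.

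A program built from that sentence would carry the same left-hollow scores under both control names. The condition that both hollows improve would then reduce to the condition that the left improves. The imputed data sets hold observed scores as well as filled-in ones, so this would reach every control subject, not only those with a missing Week 8 visit. Treated subjects would still have to improve on both sides.

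Tests 2, 3 and 4 all use the control rate, and Tests 3 and 4 reuse the imputed values from the primary analysis (SAP 6.1.1.3). All three comparisons could therefore be affected. Test 1 compares the treated rate with 50% and uses no control data.

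**Working it through.** **Step 1. The pairing.**

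| Week 8 set | Source named in the SAP | Source implied by its own name |
|---|---|---|
| `midata_8w_trt_left` | `midata_trt_left` | same |
| `midata_8w_trt_right` | `midata_trt_right` | same |
| `midata_8w_ctl_left` | `midata_ctl_left` | same |
| `midata_8w_ctl_right` | `midata_ctl_left` | `midata_ctl_right` |

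Only the fourth row is inconsistent.

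**Step 2. Direction.** Let L and R be improvement of at least one point on the left and right hollow. The defined control rate is P(L and R); the literal rate is P(L). Since P(L) ≥ P(L and R), the literal rate can equal or exceed the defined rate but never fall below it. It is equal if every control subject who improves on the left also improves on the right. The treated rate is unchanged, so the difference can only shrink. "Each test will hereby be performed at a one-sided α level of 0.025", and under the null this shift lowers the chance of rejection, so type I error is not inflated.

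**Step 3. The plan's own figures (SAP section 3).** Inputs: 70% treated, 30% control, 80 and 40 evaluable subjects, one-sided 2.5%.
- Test 1, exact binomial, n = 80: reject at 50 or more responders; power 94.1% (stated: at least 94%).
- Test 2, one-sided Fisher's exact test, 80 vs 40: power 98.4% (stated: at least 98%).
- Overall: 0.941 × 0.984 = 92.6% as a product, or 93.2% jointly (stated: above 92%).
- Drop-out: 120 / (1 − 0.20) = 150.

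The sample-size figures are sound.

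**Step 4. Power under the planned Newcombe rule.** Exact enumeration with complete data gives 99.0% for Test 2 (80 vs 40). One technique against control at 40 vs 40, that is 50 less 20% for the technique arm, gives 96.4%.

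**Step 5. Size under the literal pairing.** Left/right agreement is not in the documents, so it is assumed. With a bivariate-normal latent score and equal marginal rates, q = P(L) was solved from P(L and R; correlation ρ) = 30%:

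| Assumed ρ | Literal control rate | Excess (points) | Test 2 power | 40 vs 40 power |
|---|---|---|---|---|
| 0.7 | 42.4% | 12.4 | 84.1% | 72.6% |
| 0.8 | 39.9% | 9.9 | 89.7% | 79.9% |
| 0.9 | 36.8% | 6.8 | 94.5% | 87.2% |
| 0.95 | 34.7% | 4.7 | 96.6% | 91.0% |

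**Step 6. A second parameterisation.** Put c = P(R given L), so that the literal rate is 30% / c:
- c = 1: 30.0%, Test 2 power 99.0% (no change)
- c = 0.9: 30/0.9 = 33.3%, power 97.5%
- c = 0.8: 30/0.8 = 37.5%, power 93.5%
- c = 0.7: 30/0.7 = 42.9%, power 83.0%
- c = 0.6: 30/0.6 = 50.0%, power 58.5%

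The two approaches agree where they overlap: ρ = 0.7 corresponds to c = 30/42.4 = 0.71.

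**Step 7. Lower control rates.** With a true both-sides control rate of 20%, Test 2 power under the literal pairing is 98.6% / 99.4% / 99.8% at ρ = 0.7 / 0.8 / 0.9, and 40 vs 40 power is 95.4% / 97.3% / 98.7%. At 10% the control rate is 4.0 to 8.2 points too high for ρ = 0.9 to 0.7, and power stays above 99.8% for both comparisons.

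**The case against.** The best reply is that the intent is plain. The both-hollows rule appears in SAP 5.1.1, 6.1.1 and 6.1.1.1, imputation is ordered for each side, and the control right side has its own seed. Against these stands one repeated suffix in a note to code that the SAP itself calls only similar to what will be run. This stands, and it is why the point is minor.

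A reader might infer that the SAP plans to score the two arms by different rules, that the control right-side data are never used, or that the control rate is overstated. The documents support none of these. The stated rule is the same for both arms. The merge and responder steps cannot be seen, so only the omission of a name from one sentence is established. With full left/right agreement nothing would change.

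Planned work could also expose a coding error. SAP section 1 calls for a risk-based quality control plan. SAP 6.1.1.4 tabulates left and right scores separately for controls on observed cases, and SAP 6.1.1.3 repeats the needle and cannula comparisons on observed cases. This helps, but none of it is a direct check of the imputed control right-side set. A programmer and an independent checker who both followed the sentence would agree with each other.

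Finally, agreement between sides may be high: entry requires symmetrical hollows with equal scores (Protocol 9.2.1), and sites are asked to keep the same evaluator (Protocol 11.2.1.1). That makes the milder rows of the table plausible but does not fix the agreement at Week 8.

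**Conclusion.** The sentence is wrong as written and sits in the specification of the confirmatory analysis. It is very probably a naming slip, and it cannot be said from the public text whether the program repeats it.

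If it were followed literally, the control rate could be overstated and the treatment difference understated in Tests 2 to 4. At the 30% planning rate, with 80 and 40 evaluable subjects and assumed latent correlations of 0.7 to 0.95, the control rate would be about 5 to 12 points too high, and Test 2 power would be about 84% to 97% instead of 99%. At a control rate of 20% or less Test 2 is hardly at risk, though the reported control rate and difference could still be biased.

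The error could only work against the device. These sizes rest on an assumed left/right agreement and on complete data.

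**What to change.** In SAP 6.1.1.1, change the fourth source data set to `midata_ctl_right`. Then confirm in the program that the control right-side Week 8 set is drawn from the right-side imputation and reproduces the observed right-side scores for every control subject who has one. The cost is one word in the SAP and one quality-control check. If the program is already right, the correction simply brings the written plan into line with it.
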